6.3.7.1 Primary Analyses

The percentage of time spent in various glycemic target range will be calculated as the number of measurements in each glycemic range divided by the total number of recorded measurements. We will compare the percentage of time spent in range (100-180 mg/dL, both inclusive) in the postprandial period using Student t tests, among those randomized to NovoLog® vs. Fiasp®. Non-inferiority of Fiasp® can be confirmed if participants randomized to Fiasp® demonstrate <5% lower amount of time spent in glycemic target range compared to NovoLog®.

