6.3.7 Sample Size Considerations

Although our primary objective is to assess the non-inferiority of our intervention, we calculated power based on our secondary analysis in which we assess the superiority of our intervention because a much lower sample size is required for the non-inferiority analysis given our anticipated results.

Powering non-inferiority of our primary outcome: Using a one-sided (alpha=0.025) power calculation, we estimate that we would need a sample size of 63 participants per group to have 80% power to detect non-inferiority of Fiasp® compared to NovoLog® in postmeal time in glycemic range (100-180 mg/dl), assuming we set our non-inferiority margin at 5% less time in glycemic range and a standard deviation of 10%. A 5% non-inferiority margin was set according to an international consensus report stating that changing time in range by 5% increments would be clinically relevant. It is important to note that we have no true reference for a standard deviation of postmeal time in range for our study population, so we chose a conservative (higher than expected) standard deviation. These calculations are also conservative because they assume no hypotheses about superiority of Fiasp® (using sealedenvelope.com to calculate power).

We also estimated requiring only 63 participants to have 80% power (alpha=0.05) to detect a 2.5% greater time in glycemic range (superiority) for participants randomized to Fiasp®, compared to NovoLog® (with a 5% standard deviation of the outcome), however, we expect a greater change in percent time in range.

We will be sufficiently powered for non-inferiority (and superiority) of our primary outcome because we have chosen to power our study in order to be able to execute our secondary analysis, described below.

Powering for secondary analysis: We estimate that 80 participants per group will provide 80% power (alpha=0.05, two sided) to detect a 20 mg/dL difference in mean 24 hour (day 2) glucose between groups, assuming a standard deviation for mean glucose of 45 mg/dL, which was reported previously in a study of inpatient prandial insulin dosing (16). Previous intervention studies using CGM have reported larger differences (treatment vs. control) for time in target

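### As written, the non-inferiority rule sets the observed difference against the 5-point margin with no confidence limit, so a Fiasp arm that is worse by exactly the margin passes half the time.

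*Combined protocol and SAP*

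**What the plan says.** The Synopsis and section 4.2 make non-inferiority of Fiasp on postprandial time in range (100 to 180 mg/dL) the primary objective. Section 6.3.7.1 is the only place that says how the conclusion is reached. It compares the arms "in the postprandial period using Student t tests, among those randomized to NovoLog® vs. Fiasp", and then gives the success rule: "Non-inferiority of Fiasp® can be confirmed if participants randomized to Fiasp® demonstrate <5% lower amount of time spent in glycemic target range", relative to NovoLog. It states no null value, alpha, sidedness or confidence limit. No confidence interval is mentioned anywhere in the document.

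The only error rate tied to non-inferiority is in section 6.3.7, where the study is sized: "Using a one-sided (alpha=0.025) power calculation, we estimate that we would need a sample size of 63 participants per group" for 80% power, "assuming we set our non-inferiority margin at 5% less time in glycemic range and a standard deviation of 10"%. That section also says of the SD that "we have no true reference for a standard deviation of postmeal time in range for our study population".

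**The concern.** A non-inferiority claim needs evidence that the true deficit is smaller than the margin. The written rule asks only whether the estimated deficit is smaller than the margin, so it makes no allowance for sampling error. The t test beside it does not supply the allowance: nothing says it is run against −5, and section 6.3.7.2 uses the same test for the secondary time-in-range outcomes.

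The primary conclusion is at stake. The plan itself treats a 5-point change in time in range as clinically relevant, yet an insulin that is worse by that amount would be called non-inferior as often as not. The trial is also open-label, so a success rule that leaves its test unstated could be settled after results are known.

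**Working it through.** **Inputs.** Margin 5 points, SD 10 points, one-sided alpha 0.025, power 80% (section 6.3.7). True difference 0 for sizing, since "they assume no hypotheses about superiority of Fiasp" (section 6.3.7). Allocation 1:1 (section 6.1). Completers 80 per arm (sections 5.3.1 and 6.3.7).

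**1. Reproduce the plan's sample size.**

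n per arm = 2 × (1.960 + 0.842)² × 10² / 5² = 62.8, rounded up to 63. This matches the plan. With a one-sided alpha of 0.05 it would be 2 × (1.645 + 0.842)² × 10² / 5² = 49.5, rounded up to 50. So 63 belongs to a one-sided 0.025 test, which is the same as requiring a two-sided 95% confidence limit to clear the margin. It also treats 5 and 10 as absolute percentage points.

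**2. Precision at the planned size.**

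SE = 10 × √(2/80) = 1.581. The t critical value on 158 df is 1.975, so the 95% half-width is 1.975 × 1.581 = 3.12 points.

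**3. Chance of declaring non-inferiority at a true deficit of d points.**

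Written rule: Φ((5 − d)/SE). Confidence-limit rule: noncentral t, 158 df, lower limit above −5.

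| True deficit d | Written rule | 95% CI rule |
|---|---|---|
| 5 | Φ(0) = 50% | 2.5% |
| 6 | Φ(−0.632) = 26% | 0.5% |
| 7 | Φ(−1.265) = 10% | 0.06% |

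A simulation of 50,000 trials at d = 5 (80 per arm, SD 10) gave 50.5% and 2.5%.

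**4. A single result.**

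An observed deficit of 4.9 points passes the written rule. Its 95% interval is −4.9 ± 3.12, that is −8.0 to −1.8; t = 4.9/1.581 = 3.10, two-sided p = 0.002 in favour of NovoLog. Under a confidence-limit rule, only observed deficits below 5 − 3.12 = 1.88 points pass.

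At this precision any observed deficit between 3.12 and 5 points is both significantly worse and non-inferior under the written rule. At a true deficit of 5 points, 39% of simulated trials gave that result.

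**5. Dependence on the SD (80 per arm).** The plan uses 10 for non-inferiority and 5 in its superiority calculation for time in range. The values 15 and 20 are assumptions.

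| SD | Written rule, d = 5 | Written rule, d = 7.5 | CI rule power at d = 0 |
|---|---|---|---|
| 5 | 50% | 0.08% | >99.9% |
| 10 | 50% | 5.7% | 88% |
| 15 | 50% | 15% | 55% |
| 20 | 50% | 21% | 35% |

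**6. Could the t test rescue the rule?** Suppose a non-significant difference were required as well. A true deficit of 5 points would then still pass about 12% of the time at SD 10 and about 50% at SD 20.

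**The case against.** The strongest reply is that the plan is incomplete rather than wrong. Section 6.3.7.1 does not speak of a point estimate, it names an inferential test, and section 6.3.7 gives a margin and a one-sided 0.025. Because 63 per arm reproduces exactly under that test, a confidence-limit test was probably intended. This is fair about intent, and nothing here shows that the investigators chose a 50% error rate. But the sizing section does not say how the conclusion is drawn. The section that does leaves the alpha out, and an analyst who follows it literally would use the observed difference. The probable intent supports the correction.

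Three narrower points stand in part:

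- Only the 50% against 2.5% contrast is free of the SD. The other figures need SD 10, for which the plan admits it has no reference.
- A sound non-inferiority rule can also pass an arm that is significantly worse if precision is high. At SD 5 with 80 per arm, the confidence-limit rule would do so for observed deficits between 1.56 and 3.44 points. At SD 10 it cannot, because it stops at 1.88 and significance starts at 3.12; the written rule can.
- The corrected rule has good power only if the SD is near 10. That is a limit of the sizing assumption, not a reason to keep the written rule.

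**Conclusion.** The concern holds. The primary decision rule as written does not control the false-positive rate at which the trial was sized: 50% at the margin instead of 2.5%, a factor of 20. That figure needs only an estimator distributed symmetrically about the true difference. The 26% and 10% at deficits of 6 and 7 points, the interval of −8.0 to −1.8 and the 1.88-point threshold rest on 80 completers per arm and an SD of 10 points.

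The sample size calculation is not at fault; the defect is that its alpha is missing from the decision. Since this one sentence determines the trial's main claim, it must be corrected before the primary analysis.

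**What to change.** Replace the decision sentence in section 6.3.7.1 with:

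> Non-inferiority is concluded if the lower limit of the two-sided 95% confidence interval for mean Fiasp minus mean NovoLog in postprandial percent time in range lies above −5 percentage points (equivalent to a one-sided t test against −5 at alpha 0.025). If it does, superiority is concluded if the same lower limit lies above 0.

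The words *percentage points* settle a reading the plan leaves open. The absolute reading is the one that reproduces 63 per arm; if a relative 5% was meant, the plan must say so and the sizing must be redone. The second sentence gives the superiority objective already listed in section 4.3 a place in the sequence and costs no alpha.

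The cost is one SAP passage, with no new data. The rule is the one the trial was sized for, so it calls for no extra patients if the SD of 10 holds: power at a true difference of zero is then 88% with 80 per arm. If the SD proves larger, the interval will be wider and the trial may fail to show non-inferiority.

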6.3.7.2 Secondary Objectives Analyses

We will compare percentage of time spent in other ranges of interest as detailed in the Study Objectives using Student t tests between NovoLog® vs. Fiasp® groups. We will explore other demographic factors in modeling procedures (including age, sex, and BMI) using analysis of covariance.

In additional sensitivity analysis, we will repeat all analysis using only data from the first three meals for each patient in order to partially account for differences in hospitalization duration.

6.3.7.3 Safety/Pregnancy-related policy

See Section 7.12 Data Safety Monitoring Plan.

6.3.7.4 Analysis of Subject Characteristics

Descriptive subject variables are age, sex, race, serum creatinine and HbA1C.

6.3.7.5 Interim Analysis

There is no planned interim analysis for this study.

6.3.8 Handling of Missing Data

We anticipate minimal time periods of missing sensor data due to insufficient device attachment or device removal. These periods will be excluded from analysis. Only non-missing data will be analyzed.

7 – Trial Administration

7.1 Ethical Considerations: Informed Consent/Assent and HIPAA Authorization

Informed Consent: Study will be conducted in accordance with ICH GCP guidelines and Declaration of Helsinki. Sponsor-investigator will comply with all applicable regulatory and legal requirements in obtaining and documenting the informed consent. Sponsor-investigator will ensure that participants or their legally acceptable representative are clearly and fully informed about the purpose, potential risks and other critical issues regarding this clinical trial.

The preparation of the ICF(s) used for this study is the responsibility of the PI and must include all elements required by applicable regulatory requirements. Prior to beginning the study, the ICF(s) will be approved by the IRB. The consent form(s) used will bear the IRB stamp on all pages.

7.2 Institutional Review Board (IRB) Review

Before study initiation, the PI must have written and dated approval/favorable opinion from an IRB for the protocol, consent form/s, and any other written information provided to participants. The PI should also provide the IRB with product labeling.

The PI will provide the IRB with reports, updates and any other information according to regulatory requirements or IRB procedures.

7.3 Subject Confidentiality

Only the PI, investigators and study personnel on this project will have access to the master code. In addition, the investigators will be using password-protected computers and locked cabinets for document storage.

7.4 Deviations/Unanticipated Problems

The study shall be conducted as described in this approved protocol. Deviations or changes to the protocol shall be made only after amendment approval/favorable opinion by the IRB, except where necessary to eliminate immediate hazard to study participants. Any significant deviation will be documented in the study team progress notes and reported to the IRB per regulations.

If an amendment substantially alters the study design or increases potential risk for study participants, the Informed Consent should be revised and submitted to the IRB. Once the IRB has approved the revised Informed Consent, all study participants currently enrolled in the study must sign the amended consent, and the new consent will be used for all new participants prior to enrollment.

7.5 Data Collection

The site will perform all data management activities, including the writing of a data management plan outlining the systems and procedures to be used. Data will be collected directly from study participants or their medical records after receiving written informed consent. Data will be collected onto paper source documents and then transcribed into the study database. Study data will be accessible to study staff who are approved to work on this protocol.

Destruction of Identifiers: Paper participant records will be kept in a locked office and electronic study data will be stored in a computer database that will be password-protected and

kept on the Endocrinology shared drive. A password-protected master code list will be created that links the subjects study number to the subjects' identity. The office will be locked at all times when charts are not in use and will only be accessible to study staff. Coded data will be kept indefinitely after completion of the study.

7.6 Data Quality Assurance

The study team is responsible for the data management of this trial including quality checking of the data. For data analysis, all data will be downloaded from the electronic databases and reformatted into SPSS data sets.

7.7 Study Records

The investigator and their team will maintain adequate and accurate records that fully document the conduct of the study and enable study data to be verified. These documents should be classified into separate categories: (1) investigator's study file, and (2) participant clinical source documents.

(1) The investigator's study file includes the original protocol, protocol amendments, official data capture forms and query forms, IRB approval with correspondence, approved informed consent form, staff curriculum vitae and authorization forms, and other appropriate documents and correspondence.

(2) Participant clinical source documents include patient hospital/clinic records, physician's and nurse's notes, screening and enrollment log, etc.

The investigator and their team is required to prepare and maintain adequate and accurate case histories for each participant involved in the study. Source documents and electronic records entered in the study database must be consistent with each other, and discrepancies explained.

Corrections must be made by striking incorrect data with single line and entering correct information followed by authorized person's initials and date.

7.8 Access to Source

Clinical study data will be reported (captured) by study site personnel on paper source documents then transcribed into an electronic database.

There is no external monitor for this study. In accordance with BUMC IRB guidance, an internal quality assurance study monitor, if one is needed, will have direct access to the investigator's source documentation as needed throughout the study, in order to document compliance with the protocol and verify the completeness and accuracy of the data recorded in the official data capture forms. The Investigator and their team will cooperate with the study monitor to ensure that any problems detected in the course of these monitoring visits are resolved in a reasonable period of time.

7.9 Data Storage/Security

Paper subject records will be kept in a locked office and electronic study data will be stored in a computer database that will be password protected and kept on the Endocrinology shared drive. This storage meets BMC requirements for secure storage of PHI. A password-protected master code list will be created that links the subjects study number to the subjects' identity. The office

will be locked at all times when charts are not in use and will only be accessible to study staff. The database master code list will be deleted after completion of the study.

7.10 Retention of Records

The PI will retain all study records including the electronic database files and source documents after completion of the study. The database master code list will be kept for 7 years after completion of the study, after which it will be deleted, and coded data will be maintained indefinitely. Paper files may be stored on-site at BMC or at a secure off-site facility. The study team does not need permission from the sponsor to move or destroy the records.

7.11 Study Monitoring

An internal medical monitor (who is NOT a part of the study team) will be appointed by the PI who will review for safety (see section 7.12). Apart from this, no external or third party monitoring of this study will occur. If an internal audit is requested, the study team will cooperate per Section 7.8 Access to Source.

7.12 Data Safety Monitoring Plan

Per the OHRP Guidelines, this study is defined as "greater than minimal risk". Basal/bolus insulin regimen is the standard of care for patients with diabetes admitted to the hospital. The bolus insulin used routinely in our hospital is Humalog®. In this study, we are evaluating the effects of Fiasp® vs NovoLog®, which are being used as bolus insulin instead of Humalog®. The risks involved with administration of these two insulins are not different from the risks involved with Humalog®. Application of a CGM is a low risk procedure with minimal adverse effects. Therefore overall, this study does not have a significantly higher risk compared to the standard of care and we will not establish a Data Safety and Monitoring Board (DSMB). Study investigators will meet on a monthly basis to review study data and reported adverse events and given the risk level of the study, safety can be adequately monitored by the PI and study team.

The PI will uphold the following responsibilities:

- An internal medical monitor (who is NOT a part of the study team) will be appointed who will review for safety after the enrollment of 10 and 40 patients. Point-of-care and continuous glucose monitoring data will be reviewed. The monitor will review for any unacceptably high rates of hyper or hypoglycemia, or excessive need to deviate from the study insulin titration protocol, as well as any unexpected and/or severe events that warrant a change to the protocol.
- The PI and members of the staff will be responsible for reporting all new clinical experiences, exacerbations, and/or deterioration of any existing clinical condition occurring after a study subject has entered the study.
- The PI will be responsible for reporting Serious Adverse Events (SAEs) and Unanticipated Problems (UPs) to the BMC IRB. Per OHRP Guidelines all UPs should be reported to appropriate institutional officials (as required by an institutions written reporting procedures), the supporting agency head (or designee), and OHRP within one month of the IRB's receipt of the report of the problem from the investigator.
- The PI will be responsible for determining the causality of all AEs/SAEs subject to review by the BMC IRB.

• The PI and staff will be responsible for follow-up information on all AEs until resolution or an appropriate endpoint is reached.

The PI in concert with BUMC IRB and other study investigators will be responsible for reviewing all reports of SAEs that occur in this study and for determining whether any corrective actions need to be taken regarding: management decisions of the PI and staff, whether protocol violations are congruous with patient welfare taking precedence over protocol, whether there are any issues among the research staff that need to be addressed, etc. The study investigators will be responsible to determine if the results of its review require a revision/modification of the protocol and/or the consent form. An independent reviewer may be considered if there is potential for conflict of interest.

If any expected event listed in the consent form/protocol exceeds what it expected in terms of incidence or severity and is thought to be related to study procedures, the study will stop any procedures until more can be known about the cause of the excess.

7.13 Study Modification

The study shall be conducted as described in this approved protocol. Deviations or changes to the protocol shall be made only after amendment approval/favorable opinion by the IRB, except where necessary to eliminate immediate hazard to study participants. Any significant deviation will be documented in the study team progress notes.

If an amendment substantially alters the study design or increases potential risk for study participants, the Informed Consent should be revised and submitted to the IRB. Once the IRB has approved the revised Informed Consent, all study participants currently enrolled in the study must sign the amended consent, and the new consent will be used for all new participants prior to enrollment.

7.14 Study Discontinuation

The treatments used in this study fall within accepted clinical practice. However, if severe unanticipated adverse events do occur, then the study will be stopped.

7.15 Study Completion

Data collection is expected to be completed by the end of 2022. When all data and sample analyses are completed, the study will be closed with the BUMC IRB per local guidelines.

7.16 Conflict of Interest Policy

Per BMC policy number 09.04.000, all study investigators are required to disclose any relationships that may create a potential conflict of interest to BMC using an approved institutional Conflicts of Interest form. This occurs at least once per year. Any actual or perceived conflicts of interest are managed by the BMC Compliance Department.

7.17 Funding Source

This study is funded by Novo Nordisk, Bagsvaerd, Denmark.

7.18 Publication Plan

We will submit study results for oral presentation at national conferences in Endocrinology as well as for publication in a major high impact peer-reviewed journals in that same area after

embargo has been lifted. All presentations and publications will acknowledge the funding source.

Appendix 1. Insulin initiation protocol

Initial insulin dose:

Determine initial TDD using baseline estimate and subtracting of adding for each risk factor:

Baseline TDD estimate	Start at 0.5 units/kg/day
Age >70 years old	-0.1 unit/kg/day
If renal insufficiency	-0.1 unit/kg/day
If pancreatic deficiency	-0.1 unit/kg/day
If HbA1c >10%	+0.1 unit/kg/day
FINAL TDD ESTIMATE	=

Basal dose: Give 50% of dose as insulin glargine every 24 hours.

Prandial dose:

Divide the remaining 50% of TDD by 3 and order for each meal. Round up (for decimals 0.6 and above) or down (for decimals 0.5 and below) to nearest whole number.

For Group 1: Order prandial insulin as NovoLog®

For Group 2: Order prandial insulin as Fiasp®

Correction dose:

Take 1500/TDD = correction factor. Patients will have correctional scales built for BG 150-300 mg/dL starting at 150 mg/dL premeal and at 200 mg/dL before bedtime. Doses will start at 2 units.

For Group 1: the correction dose will be given as NovoLog® insulin in addition to the patients' scheduled premeal prandial dose.

For Group 2. The correction dose will be given as Fiasp® insulin in addition to the patients' scheduled premeal prandial dose.

At the discretion of the study team, patients with fasting hypoglycemia or judged to be at risk for fasting hypoglycemia may have an additional correction scale ordered for 2AM.

BG monitoring: BG will be measured before each meal using bedside point-of-care meters and at bedtime (9 pm) daily. BG may also be measured if patient experiences symptoms of hypoglycemia, to assure correction of hypoglycemia, and if requested by a physician.

